Stress. The PSS is the most widely used psychological instrument for measuring the perception of stress. The original version, published in 1983,^{72,73} has been refined over the years into its current form and is available a public domain instrument. It measures the degree to which situations in one's life are appraised as stressful. Items were designed to tap how unpredictable, uncontrollable, and overloaded respondents find their lives. The items are easy to understand and general in nature, and hence relatively free of content specific to any subpopulation group. PSS scores are correlated with self-reported health, health behaviors, smoking status, and help seeking behavior.⁷³ The PSS exhibits excellent construct validity and reliability.⁶⁶

Sleep & Rest/Activity Rhythms. Wrist actigraphy is a non-invasive, quantitative, and validated method that will provide a primary means by which circadian disruption is assessed in this study. Weekly actigraphic monitoring will be performed once each at baseline, post-treatment, and at the 8-week follow-up using a standardized protocol.^{14,74-76} Actiwatch-Spectrum monitors (with built-in ambient multiple spectrum light sensor, event marker, digital watch, and off-wrist detection capability, Respironics, Bend, OR) will be used in this study. They are similar in size, weight, and appearance to a wristwatch. Monitors will be worn on the non-dominant wrist, recording activity and light exposures at 1-minute intervals. Subjects will wear the monitors 24-hours per day for three 1-week intervals (baseline, post-treatment, and at the 8-week post-training follow-up). Participants will be asked to follow their usual sleep-wake schedules and maintain a log of when they go to bed and awaken on days when they wear the actiwatch. At the end of each 1-week actigraphic monitoring period, a study technician will retrieve the monitor from the subject during their weekly training session. Alternatively, participants can mail the actiwatch to research staff using a pre-labeled, postage-paid envelope that will be provided to the participants, or a study investigator can retrieve the monitor from the individual's residence. These methods have all been successfully implemented in previous studies among DVAMC patients and elsewhere.^{14,77} Actigraphic sleep parameters have been previously validated,^{67,68,78,79} and 1-week intervals provide for ample sleep or rest/activity rhythm assessment.⁷⁹ A weekly average of sleep metrics (latency, duration, efficiency, fragmentation, wake time after sleep onset [WASO], daytime nap duration) will be quantified using the manufacturer's accompanying software (Appendix II).

Sleep disruption will be ascertained using the Pittsburgh Sleep Quality Index (PSQI), which is a self-administered 19 question instrument, categorized into 7 components, that assesses sleep duration as well as latency, frequency, and severity of sleep problems with a possible range of 0-21. The 7 components are subjective sleep quality, sleep latency, sleep duration, habitual sleep efficiency, sleep disturbances, use of sleep medication, and daytime dysfunction. The Cronbach's alpha coefficient for all component scores was 0.83 which indicates high internal consistency. Those with disorders of initiating and maintaining sleep and with disorders of excessive somnolence had statistically significantly higher scores compared to control subjects, which indicates good construct validity. A cut-point score of 5.0 indicated a sensitivity of 90% and a specificity of 87% in identifying those with a sleep disorder.⁸⁰ One advantage of the PSQI over other instruments is that it provides information on overall subjective sleep quality and includes several items related to snoring and the induction of sleep apnea or hypopneas, which can influence heart rate, a primary study outcome. We will modify the time scale for reporting on sleep quality to the previous week to coincide with planned wrist actigraphy measures. We will augment the use of this instrument by performing CPRS queries for each participant (with a HIPAA release) to identify diagnostic codes for insomnia or other sleep disorders.

Using actigraphy data, insomnia may be defined using the following cut-off values: sleep onset latency ≥ 12 minutes, total sleep time ≤ 440 minutes, WASO ≥ 25 minutes, sleep efficiency $\leq 92\%$, or the number of 5-minute wake episodes ≥ 2 .⁶⁹ The phase and amplitude of circadian rest/activity rhythms will be characterized via previously described non-parametric (interdaily stability, intradaily variability, relative amplitude, 24-hour autocorrelation coefficient) and cosinor statistics (acrophase, mesor, amplitude, amplitude/mesor ratio, goodness of fit).^{67,68,81} Ambient light exposures collected via actiwatches will be summarized using the same descriptive, cosinor, and nonparametric statistics.

Ambulatory Heart Rate Variability Monitoring. In a limited number of participants, a convenience sample (n=15-30 total) will be asked to wear a data-logging ambulatory heart rate monitor (Firstbeat Bodyguard 2; Firstbeat Technologies, Jyväskylä, Finland) for two 1-week periods that coincide with data collection for the wrist activity monitor (i.e., at baseline and during the post-training week). The heart monitor is lightweight, portable and noninvasive (see photo). It attaches to the skin with a snap electrode and does not require a belt around the body. There is no need for the participant to operate or adjust the monitor in any way, they only need to wear it. Note: it should be removed when taking a shower, or while bathing or swimming (extra skin patch electrodes will be provided to re-attach the device). Participants will wear this device 24 hours per day. The data record allows for time- (mean and std HR, NN50, pNN50, and RMSSD) and frequency-domain variables (VLF, LF and HF power, peak frequency, peak frequency power, and coherence) to be generated for comparison with actigraphic sleep data and other exploratory research. Research staff will hand out and collect both the heart rates and wrist actigraphy monitors at the same time for each participant. Data are downloaded for processing with a cable attached to the computer's USB port, and the battery is recharged in a similar manner. Participants will be provided with written and verbal instructions on appropriate use (no showering, bathing or swimming) and with extra leads for re-attaching the monitor after showering, etc.

Depression & Fatigue will be ascertained using several valid instruments. Fatigue will be assessed using the Multi-Dimensional Fatigue Inventory (MFI), comprised of 20 questions that assess general, physical, and mental fatigue, and reduced motivation and activity. It also has good internal consistency (Cronbach alpha: >0.75) and high convergent validity confirmed via strong correlations with several other validated instruments.^{82,83} Depressive symptoms will be ascertained using the Beck Depression Inventory II (BDI-II).⁸⁴⁻⁸⁶ The BDI-II is a 21-item self-report instrument that assesses the existence and severity of symptoms of depression as listed in the American Psychiatric Association's Diagnostic and Statistical Manual of Mental Disorders, Fourth Edition (DSM-IV). The BDI-II has excellent clinical sensitivity (Cronbach alpha: 0.92).⁸⁴ Its construct validity has been established, and it readily differentiates depressed from non-depressed patients.⁸⁷

Cognitive Performance. A short and simple battery consisting of three validated neuropsychological tests will be administered at the 4 test periods: the Paced Auditory Serial Addition Test (PASAT), the Hopkins Verbal Learning Test (HVL), and the Psychomotor Vigilance Test (PVT). These PASAT and HVL have alternate forms and the PVT has no significant practice effect. This battery of assessment instruments has sufficient reliability to detect changes over repeated test sessions. Brief descriptions are provided below.

Paced Auditory Serial Addition Test (PASAT). The PASAT is a measure of cognitive function that assesses auditory information processing speed and flexibility, as well as calculation ability. It was developed in 1977 and is now very widely used in clinical and research applications to assess cognitive function. In the PASAT, single digits are presented every 3 seconds and the patient must add each new digit to the one immediately prior to it. Several alternate forms have been developed that are publically available to minimize familiarity with the stimulus items when the PASAT is repeated on more than one occasion. Administration time is approximately 5 minutes. The score for the PASAT is the total number correct out of 30 possible answers. The PASAT has demonstrated high split-half reliability and evidence for convergent and divergent validity with good sensitivity for deficits in the areas of auditory information processing speed and flexibility.

Hopkins Verbal Learning Test. The HVL is a measure of verbal learning and memory, in which the participant is presented with a list of 12 semantically categorized words and is asked to recall as many as he/she can. This process is repeated twice more, and the score is equal to the total number of words recalled across all three trials. The test takes approximately 5-10 minutes to administer. There are several alternate versions to eliminate practice effects across repeat test sessions. The norms are in the public domain and available without cost.

Psychomotor Vigilance Task (PVT). The psychomotor vigilance task (PVT) is a widely used and well-validated test of sustained-attention and reaction-time that measures the speed with which subjects respond to a visual stimulus. The PVT correlates with lowered alertness, slower problem-solving, decreased psycho-motor skills, and increased rate of false responding. The PVT is popular because of its ease of administration and scoring, simple metrics, and convergent validity. The PVT is a simple task where the subject presses a button as soon as a light appears on the computer screen. The light will turn on randomly every few seconds for 5 minutes. The main measurement of this task is to assess reaction time and how many times the button is not pressed when the light is on. The purpose of the PVT is to measure sustained attention, and give a numerical measure of level of arousal. The program is publically available at no cost.

Lifestyle and sociodemographic characteristics will be assessed using instruments developed in our previous studies among Veterans.^{44,77,88} Chronotype refers to the self-reported characterization of individuals with inherent morning or evening preference (or neither).^{89,90} This trait has been associated with intrinsic circadian period,⁹¹ and the circadian timing of numerous psychophysiological processes,⁹²⁻⁹⁵ including sleep,^{96,97} arousal and alertness,⁹⁸ mood,⁹⁹ and the secretion of catecholamines,¹⁰⁰ and cortisol.¹⁰¹ The Munich Chronotype Questionnaire (MCTQ)¹⁰² will be used to ascertain self-reported chronotype and sleep/wake timing on free and work days. Disparities between chronotype and social schedules can result in chronically desynchronized sleep-wake timing or 'Social Jetlag',^{103,104} which will be quantified as the absolute difference between mid-sleep on weekdays and weekends, after adjusting for weekend make-up sleep.¹⁰⁴ Other potential modifiers of the HRV-B treatment that will be assessed include: social support,¹⁰⁵ and coping.¹⁰⁶

Saliva Specimens. Saliva samples (~1/2 tablespoon) will be collected by each participant; once at baseline, once at the post-treatment assessment, and another at the final follow-up visit. One ~2 mL saliva sample will be collected each time using the simple, noninvasive passive drool method with Oragene® DNA collection kits (model: OGR-500, DNA Genotek, Ontario, Canada, <http://www.dnagenotek.com>).¹⁰⁷ The vial has a fill line for precise volume collection, and salivary DNA is immediately stabilized by a preserving reagent. Samples will be frozen at -80°C for long term archive. DNA can be purified from the archived specimens using a standard ethanol precipitation method from commercially available kits. The median yield for a 2 mL sample using this device is 110 µg DNA. Good quality DNA will be defined as a 260/280 UV absorbance ratio of 1.7-2.0. These

specimens will serve as a valuable resource for future research targeting biological processes that may mediate or modify the treatment effect. Another ~2 mL native saliva sample (without added reagent) will be collected for recovery of proteins or peptides using the same collection procedure.

The samples will be archived in frozen storage for future research. Samples will be coded with a unique number that will not include participant's name or any other personal information. Only the Principal Investigators, or a study Co-Investigator, will have access to the code that links the sample to their identity. The samples will be stored indefinitely in a -80C freezer for future research purposes at the DVAMC Building 9A, basement. Analyses that are under consideration include the study of genes involved in pain or other study endpoints, or responses to the HRV-B treatment. This may include candidate gene or genomic sequences, gene expression, or genetic modifications (e.g., epigenetic changes, sequencing). Analyses may also include immune system markers, hormones, or other compounds or microbes (e.g., bacteria) in saliva. Some sample analyses will be performed in the laboratory of [name], [name]. Sample analyses also will be performed by EpigenDx, [name]. These measures will be for exploratory research and not for clinical use. Therefore, individual results will not be provided to participants. Use of these samples for future research is noted on the consent document.

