Pain initiates a stress response that increases sympathetic output and facilitates autonomic imbalance. Heart rate variability (HRV) is a valid, quantitative, noninvasive measure of autonomic function. HRV biofeedback (HRV-B) is a novel biobehavioral procedure whereby patients learn to restore autonomic imbalance by developing 'HRV coherence'. Patients in this state have improved mood, cognition, and executive function, and HRV-B interventions have been used to treat: pain, anxiety, depression, insomnia and symptoms of posttraumatic stress disorder (PTSD) and heart disease. We have found that HRV-B training among Veteran PTSD patients can enhance HRV coherence and improve cognition and sleep relative to controls. Importantly, our pilot study showed that HRV-B can alleviate chronic pain and stress among Veteran Pain Clinic patients. HRV-B thus has a pivotal role in restoring autonomic balance and managing pain and the symptoms that amplify it. The proposed project is a randomized, sham-controlled, biobehavioral intervention that will test the hypotheses that HRV-B increases HRV coherence and reduces pain, stress, fatigue, insomnia and depression and improves sleep, activity, and cognition. Because this is a behavioral intervention, it is difficult to blind the subjects to the active vs sham treatment, and the biofeedback coach who provides the training must know the condition to which the subject is assigned. However, all others in the study are blinded to the training. The specific aims are: 1.) Determine whether HRV-B increases HRV coherence and reduces pain or stress relative to a sham treatment among Veterans with chronic, nonmalignant, axial neuromusculoskeletal pain; 2.) Determine as an exploratory aim whether HRV-B reduces insomnia, fatigue or depressive symptoms, and increases sleep and activity and improves cognition among patients relative to sham treatment. We hypothesize that HRV-B will (1) reduce self-reported pain and stress ratings, (2) improve objective measures of actigraphic sleep parameters (sleep latency, duration, efficiency, fragmentation), rest/activity rhythms (dichotomy index, interdaily stability) and cognitive function (reaction time, attention); and (3) alleviate self-reported fatigue and depression symptoms. Patients from both groups will be randomized to our previously established HRV-B or sham protocol (n=40 each), and will complete a baseline assessment, 6 weekly training sessions, a post-training assessment, a 4-week booster training and assessment, and an 8-week post-training follow-up evaluation, for a total of 10 visits to the research site. Portable, hand-held, data-logging devices will be used to practice attaining HRV coherence at home by the active treatment group, while those in the sham training group will get a 'stress squeeze ball'. Standard methods will quantify HRV coherence and other HRV measures, and validated instruments will be used to assess pain and stress. Wrist actigraphy is a valid, quantitative, and noninvasive procedure that will be used to characterize insomnia via continuous recordings collected 24-hrs/day over three 1-week periods (at the baseline, post-treatment, and 8-week follow-up assessment). A small battery of tests measuring attention and reaction time will assess changes in cognitive performance. Data analyses will apply linear models for repeated measures to evaluate the effect of HRV-B on study outcomes, and on treatment persistence, after adjusting for confounding factors. For each measure we will calculate three estimates of change for each patient (post-training minus pre-training, 4-week booster minus post-training, and 8-week follow-up minus the 4-week booster assessment). Path analyses will examine direct and indirect relationships between HRV-B, the primary and exploratory outcomes, and personal or social factors that may modify these relationships. This study will be the first to examine HRV-B for pain management among Veteran chronic pain patients. This study is directly responsive to a national VHA/DoD Task Force's recommendations to provide complementary, integrative therapies for pain management to Veterans.

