Recruitment will follow a multi-step process of: 1.) obtaining a HIPPA wavier to identify active patients who are eligible for the study based on inclusion and exclusion criteria; 2.) informing potential participants of the nature of the study by letter, and excluding those who decline from the potential participant list; 3.) for those who do not decline, making a follow-up telephone call to ascertain interest in study, and if the patient expresses interest in the study; 4.) screening them during the same telephone call for chronic pain and any other inclusions and exclusions not ascertained from the medical record; and 5.) obtaining informed consent from patients eligible and willing to participate. The PIs will obtain a HIPPA wavier to access the docket of patients with a new or current pain diagnosis (within 6 months). This list will be narrowed to eligible patients based on medical record review. A staff recruitment coordinator will be responsible for patient screening and recruitment.

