Random Assignment to the 6-week HRV-B treatment or sham intervention group will occur following the baseline assessment. We will use a permuted block randomization procedure, with a block size of 4 and no stratification. Thus, for example, assuming 20 patients are to be assigned either to Sham (S) or Biofeedback, there would be 20 blocks of 4 patients, and two patients will be assigned each to the (S) treatment and two to the biofeedback by randomly selecting one of six possible permutations of the two treatments in blocks of four. The order of the blocks will be randomly generated. The treatment assignment will be determined before any patient is enrolled into the study and the documentation and assignment of patients will be kept confidential and known only to the PI ([name]). Only the Biofeedback professional, who delivers the treatment, will know the treatment status of the participant; other study personnel will be blinded to treatment status.

HRV-B Training. HRV-B training will follow our previously established, standardized protocol that is consistent with recommendations of the Biofeedback Certification Institute of America (BCIA), consisting of a 15-minute resting period that includes HRV recording, and a 25-minute biofeedback training and coaching or sham period. The resting periods are the same for both the HRV-B treatment and sham groups. Participants will be affixed with HRV monitoring equipment and will be instructed to sit quietly for 15 minutes in a relaxed posture, viewing a static nature scene on a computer monitor, without any instruction, coaching or biofeedback. Coaching or instruction will start after the 15-minute resting period. Patients in the sham condition will be asked to 'just relax' or 'take it easy' for the remainder of the 25-minute session. Patients in the HRV-B group will be coached on how to achieve HRV coherence.

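### As written, a PI knows all 80 assignments before enrolment, although the protocol calls all staff except the biofeedback professional blinded, and no release step is described

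*Combined protocol and SAP*

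**What the plan says.** The Random Assignment paragraph of section 2.2 specifies permuted blocks "with a block size of 4 and no stratification", with assignment following the baseline assessment. On timing of the sequence it says: "The treatment assignment will be determined before any patient is enrolled into the study". On custody, the same sentence goes on: "documentation and assignment of patients will be kept confidential and known only to the PI". The next sentence reads: "Only the Biofeedback professional, who delivers the treatment, will know the treatment status of the participant; other study personnel will be blinded to treatment status".

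The opening abstract concedes that subjects are hard to blind and that the coach must know the condition, and then adds: "all others in the study are blinded to the training".

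On the PIs' other duties, section 2.1 states: "The PIs will obtain a HIPPA wavier to access the docket of patients with a new or current pain diagnosis". That list is then narrowed by record review. Section 2.4 has the PIs monitor progress and participant safety and check accrual and attrition each week. It also has the Co-PIs contacted at once about adverse events, and allows either PI to recommend suspending the study.

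Section 2.1 gives screening, the eligibility criteria and recruitment to a recruitment coordinator, not to a PI.

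**The concern.** Two adjacent sentences each use the word only, and each names a different role as the one that knows. If the custody sentence is followed, an investigator holds every future assignment from the first day and is not blinded. If the second sentence and the abstract are followed, no investigator other than the biofeedback professional should know any assignment. Nothing in the protocol (envelopes, a central service, an independent holder or a hand-over step) shows how both could be met in practice.

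This matters more here than in a trial with strong masking. Pain and stress, two of the three primary endpoints, are self-reported, and the protocol admits that patient blinding is difficult. Concealment before assignment and blinding of the investigators after it therefore carry much of the protection that remains. A list holder who also has access to the patient docket, follows attrition weekly and handles adverse events could influence who is approached, how hard a participant is retained or how an event is judged, without intending to.

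**Working it through.** The point concerns who knows what and when, so the main check is a comparison of statements. The only arithmetic is the size of the list.

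**Size of the list.** The paragraph refers to six possible permutations of a block. With two patients per arm in a block of four, 4!/(2! × 2!) = 6, which agrees. It also gives 20 blocks: 20 × 4 = 80, which matches 40 + 40 in the specific aims. (The same sentence speaks of 20 patients; 20/4 would be 5 blocks, so that wording needs correcting too.) The sequence is complete before enrolment, so its holder knows 80 of 80 assignments in advance.

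**Statements side by side.**

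| Source | Who knows assignments |
|---|---|
| Section 2.2, custody sentence | The PI only, for the whole sequence, before enrolment |
| Section 2.2, next sentence | The biofeedback professional only; other personnel blinded |
| Abstract | The coach must know; all others blinded |

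**Possible readings.**

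1. *Literal, two people.* The first row contradicts the second and third.
2. *The PI as custodian who tells the coach each assignment after baseline.* The two uses of only can then be read as custody and delivery. But the PI still knows 80 of 80, so the statement that other personnel are blinded is false for that PI, and the release step is not written down.
3. *The PI and the biofeedback professional are the same person.* The two sentences then agree. That person would still hold all 80 assignments before enrolment, and concealment would still be undescribed. Names are removed, so this cannot be tested. The Data Accuracy and Protocol Compliance paragraph of section 2.4 lists the biofeedback professional and the Co-PIs as separate parties, which points to two people but does not settle it.

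Under every reading, a PI has advance knowledge of the full sequence and no concealment procedure is stated.

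**Is the list holder remote from the trial?** Sections 2.1 and 2.4 assign docket access, the weekly accrual and attrition checks and safety monitoring to the PIs jointly. The list holder is one of the PIs, so those duties cover that person.

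**The case against.** The strongest reply is that the second reading is the natural one: one sentence is about custody, the other about who knows a participant's status while treating. That is fair, and it means the text may be loosely worded rather than wrong in conduct. It does not make the custodian PI blinded.

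A second reply is that the PIs' part in patient identification is thin. Obtaining a waiver is a regulatory step, the narrowing of the list is written in the passive, and checking accrual does not decide who is enrolled next. This also stands in part. A reader might infer that the person recruiting can see the list. The documents do not support that, because the recruitment coordinator does the screening and falls among the blinded personnel of section 2.2. Consent, screening and baseline also precede assignment.

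A third reply points to other safeguards: a time-matched sham, asking patients which condition they think they are in, double data entry, a locked dataset, intention to treat, a comparison of participants with non-participants, and HRV coherence as a physiological endpoint. These are useful, but none of them conceals the list. The non-participant comparison would not detect selection that differs by arm.

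Two further inferences are tempting and should not be drawn.

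- *That the PIs decide how missing data are handled.* The Missing Data paragraph of section 2.3 names only the integrated team.
- *That the fixed block size makes assignments guessable to recruiters.* For someone who knows every past assignment, the chance of a correct best guess over the four positions is (1/2 + 2/3 + 2/3 + 1)/4 = 70.8%. But the documents name only two such people. The PI already has the whole list, and the biofeedback professional is not described as enrolling anyone. Mixed blocks would hardly help: with sizes 2, 4 and 6 equally likely the figure is (2 × 0.750 + 4 × 0.708 + 6 × 0.683)/12 = 70.3%.

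**Conclusion.** The point holds as a gap in allocation concealment and investigator blinding. By the protocol's own wording, a PI with joint duties in patient identification and in monitoring knows 80 of 80 assignments before enrolment, while the next sentence and the abstract describe that PI as blinded. No procedure for passing an assignment to the biofeedback professional is given.

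The documents do not show that anyone who screens or recruits has access to the list, or that any bias has occurred. The size of a possible bias cannot be estimated from them.

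The conclusion rests on one assumption: that the PI in the Random Assignment paragraph is one of the PIs to whom sections 2.1 and 2.4 give their duties. If that PI is also the biofeedback professional, the conflict over blinding falls away, but the advance knowledge and the missing concealment step remain. Confidence is high for the conflict in wording and lower for any practical consequence. Sample size and power are unaffected. The change should be made.

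**What to change.** In the Random Assignment paragraph, replace the statement that the list is known only to the PI. State instead that:

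- an existing person with no role in recruitment, assessment, monitoring or analysis generates and holds the sequence. This could be research-office staff, or a university biostatistician who is not an analyst on this trial (the Data Security paragraph of section 2.3 allows analysis under an agreement with the university's biostatistics department, so this condition matters);
- each assignment is released to the biofeedback professional only after that participant's baseline assessment is complete, with the release recorded;
- the PIs are blinded, so that section 2.2 and the abstract agree. If a PI is also the biofeedback professional, say so and describe that person as unblinded.

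The block size can stay as it is. The cost is a change of wording and a minor administrative handover, with no change to sample size, visits or analysis. If the trial is already run this way, the correction simply documents it.
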